11.5. Clinical Laboratory Evaluations

11.5.1. Hemolysis Data

The operational definition of IGIV-associated hemolysis for this analysis is defined as any event meeting the following criteria occurring within 10 days following IGIV administration:

- (a) A fall of at least 1 g/dL in hemoglobin from the previous value;
- (b) A positive Coombs test (direct anti-globulin test); and
- (c) At least 2 of the following: increased reticulocyte count, increased lactic dehydrogenase (LDH), low haptoglobin, increased bilirubin, increased plasma free hemoglobin, increased urine hemosiderin.

Data on potential IGIV-associated hemolysis will be summarized by cohorts and age groups for the CP and IMP Treatment Periods.

Additionally, as requested by FDA, a listing of hemolysis-related analytes across time for subject with >1 g/dL fall in hemoglobin from the mean of Screening and pre-IMP baseline values will be provided. Hemolysis analytes include urine hemosiderin, serum haptoglobin, plasma free hemoglobin, direct coombs test, LDH, and bilirubin.

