- Provide data on adverse events, including episodes of hemolysis or thrombosis, as well as immunologic testing (anti- β 2GPI and anti- β 2GPI-DI antibodies) in subjects currently receiving commercially licensed IGIV product, as well as in subjects receiving the IMP.

This schema for the staggered administration of IMP will result in the following two time periods for each individual subject:

Waiting Period: This is the elapsed time from enrollment to the first administration of IMP. During this time period, subjects will receive either their current commercially licensed product (CP) or a CP chosen by the Principal Investigator in consultation with their treating physician. All relevant safety and efficacy endpoints will be recorded and summarized for this time period.

IMP Treatment Period: For each subject, this is the elapsed time from the first administration of IMP to study completion. During this time period, subjects will receive the IMP, ProMetic BioTherapeutics Immune Globulin Intravenous (Human) 10%. All planned safety and efficacy endpoints will be recorded and summarized for this time period. All primary and secondary efficacy analysis is restricted to data collected during this time frame.

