6.9 Hemolysis

Tests for hemolysis include urine hemosiderin, serum haptoglobin, plasma free hemoglobin, Coombs test (direct anti-globulin test).

Samples for hemolysis assessments will be collected at the following time points:

- **All subjects** at Screening
- **All subjects** before administration of IMP or CP at infusions 1 (baseline value), 2, 3 and 4 and then every fourth infusion (8, 12, 16, etc.), TCTV and at the LTSV
- **Post-Infusion IMP treatment for Groups 1 and 2** during Safety Evaluation Phase
 - 2-3 days after administration of IMP after administration of IMP infusions 1 (baseline value), 2 and 4;
 - 7 days (± 1 day) after administration of IMP at infusions 1, 2, and 4 and then after every fourth infusion (8, 12, 16) until IMP treatment ends;
- **Post-Infusion IMP treatment for Group 3**
 - 7 days (± 1 day) after administration of IMP at infusions 1 and 4

If it is difficult for subjects (particularly children) to return to the study site for these tests, blood samples may be drawn by a home healthcare nurse.

For all subjects, a drop of ≥ 2.0 g/dL from the pre-infusion hemoglobin level or clinical signs of hemolysis between visits will lead to a full hemolysis work-up.

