- q Pre-infusion hemolysis laboratory tests will include urine hemosiderin, serum haptoglobin, plasma free hemoglobin, Coombs test (direct anti-globulin test). Pre-infusion hemolysis testing will be done for all subjects before administration of CP at infusions 1 (baseline value), 2, 3, 4 and then every fourth infusion (8, 12, 16, etc.). For all subjects, a drop of ≥ 2.0 g/dL from the pre-infusion hemoglobin level or clinical signs of hemolysis between visits will lead to a full hemolysis work-up (Section 6.9).
- r Screening visit will include demographics. Subjects treated with commercial IGIV or IGSC may receive their current treatment infusion either before the screening visit or at the screening visit if screening laboratory samples are taken prior to the infusion. Subjects receiving IGSC when they enter the study will have their screening visit up to 17 days prior to the Baseline Visit.

Table 4. Schedule of Assessments and Study Events for IMP Treatment

	Baseline		Treatment with IMP															TC ^a	LTSV ^{bb}
Visit/Infusion	Screen Visit ^{aa}	IMP 1 ^e	IMP 2	IMP 3	IMP 4	IMP 5	IMP 6	IMP 7	IMP 8	IMP 9	IMP 10	IMP 11	IMP 12	IMP 13 ^b	IMP 14 ^b	IMP 15 ^b	IMP 16 ^b	IMP 17 ^c	Standard 18 ^d
Week (21-day cycle)	-3 weeks	0	3	6	9	12	15	18	21	24	27	30	33	36	39	42	45	48	51
Visit/Infusion	Screen Visit ^{aa}	IMP 1 ^e	IMP 2	IMP 3	IMP 4	IMP 5	IMP 6	IMP 7	IMP 8	IMP 9	IMP 10	IMP 11	IMP 12	-	-	-	-	IMP 13 ^c	Standard 14 ^d
Week (28-day Cycle)	-4 weeks	0	4	8	12	16	20	24	28	32	36	40	44	-	-	-	-	48	52
Pre-infusion																			
Medical History and prior ADRs to IgG	X																		
Concomitant medications	X	X	X	X	X	X	X	X	X	X	X	X	X	X	X	X	X	X	X
Review eligibility criteria	X	X																	
Subject diary review		X	X	X	X	X	X	X	X	X	X	X	X	X	X	X	X	X	X
Vital signs	X	X	X	X	X	X	X	X	X	X	X	X	X	X	X	X	X	X	X
Physical examination ^g	X	X	X	X	X	X	X	X	X	X	X	X	X	X	X	X	X	X	X
Weight ^h		X	X	X	X	X	X	X	X	X	X	X	X	X	X	X	X	X	X
Urine pregnancy test ⁱ	X	X	X	X	X	X	X	X	X	X	X	X	X	X	X	X	X	X	X
IgG trough levels ^j	X	X	X	X	X	X	X	X	X	X	X	X	X	X	X	X	X	X	X
Anti-β2GPI and Anti-β2GPI-DI ^k	X	X	X		X				X										X
Retention sample for immunogenicity ^l		X	X	X	X	X	X	X	X	X	X	X	X	X	X	X	X	X	X

	Baseline		Treatment with IMP															TC ^a	LTSV ^{bb}
Visit/Infusion	Screen Visit ^{aa}	IMP 1 ^e	IMP 2	IMP 3	IMP 4	IMP 5	IMP 6	IMP 7	IMP 8	IMP 9	IMP 10	IMP 11	IMP 12	IMP 13 ^b	IMP 14 ^b	IMP 15 ^b	IMP 16 ^b	IMP 17 ^c	Standard 18 ^d

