Data on potential IGIV-associated hemolysis will be tabulated and discussed in the text. The operational definition of IGIV-associated hemolysis for this analysis is defined as any event meeting the following criteria occurring within 10 days following IGIV administration: (a) a fall of at least 1 g/dL in hemoglobin from the previous value; (b) a positive Coombs test (direct anti-globulin test); and (c) at least 2 of the following: increased reticulocyte count, increased LDH, low haptoglobin, increased bilirubin, increased plasma free hemoglobin, increased urine hemosiderin.

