11. EVALUATION OF SAFETY PARAMETERS

Evaluation of safety includes the analysis of treatment-emergent adverse events (TEAEs) and the analysis of laboratory investigations.

All TEAEs experienced will be recorded during the study and coded using the Medical Dictionary for Regulatory Activities (MedDRA) version 17.0. Details to be collected include TEAE diagnosis, date and time of onset and resolution, whether the event is ongoing, whether the event is serious, frequency, severity, outcome status, action taken and relationship to study drug (IMP or CP).

Safety endpoints measured during both the CP Treatment Period and the IMP Treatment Period will be summarized side-by-side using the appropriate descriptive statistics.

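### The CP and IMP hemolysis summary applies a 10-day laboratory definition to periods that are tested very differently, and it states no denominator

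*SAP*

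**What the plan says.** SAP 11.5.1 defines IGIV-associated hemolysis as "any event meeting the following criteria occurring within 10 days following IGIV administration". The criteria are a hemoglobin fall of at least 1 g/dL, a positive Coombs test, and at least two of six further markers. Protocol 12.3.4 uses the same definition. The planned output is: "Data on potential IGIV-associated hemolysis will be summarized by cohorts and age groups for the CP and IMP Treatment Periods". SAP 11 adds: "Safety endpoints measured during both the CP Treatment Period and the IMP Treatment Period will be summarized side-by-side using the appropriate descriptive statistics". SAP 11.5.1 gives no rate and no denominator.

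The testing schedule is in Protocol 6.8, 6.9 and 7.1:

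- **CP.** Table 3, footnote q: "Pre-infusion hemolysis testing will be done for all subjects before administration of CP". Footnote j sets the same pre-infusion timing for hematology, chemistry and urinalysis. The only post-infusion laboratory rows in Table 3 are d-dimer and the protein C and S retention sample.
- **IMP, Groups 1 and 2.** General and hemolysis panels are drawn 7 days after infusions 1, 2, 4, 8, 12 and 16. A hemolysis panel is also drawn 2 to 3 days after infusions 1, 2 and 4.
- **IMP, Group 3.** The 7-day panels are drawn only "after administration of IMP at infusions 1 and 4".

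Protocol 3.1 lists, among the purposes of the scheduling scheme: "Provide data on adverse events, including episodes of hemolysis or thrombosis", for subjects on commercial product as well as on IMP.

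**The concern.** The case definition can be met only if the right blood tests are done within 10 days of an infusion. The schedule provides such tests after some IMP infusions and after no CP infusion. A side-by-side table therefore compares periods with different chances of finding a case. If the true risk were the same, IMP would tend to look worse.

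The same problem arises within the IMP column. SAP 11.5.1 splits by cohort and age group but not by scheduling group. Testing intensity depends on scheduling group, and every child is in Group 3. A lower figure in children could simply reflect fewer tests.

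Because the denominator is not stated, the IMP figure could also be computed in ways that mean different things. Protocol 12.3.1 summarizes counts as rates per subject per infusion. SAP 6.1 summarizes categorical data as percentages of subjects.

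**Working it through.** **Infusions per subject.** IMP infusions run from Week 0 to Week 48. On the 21-day cycle, 48/3 + 1 = 17. On the 28-day cycle, 48/4 + 1 = 13. Both agree with footnote c of Protocol Table 4.

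**When CP samples fall.** A pre-infusion sample is taken at the next visit, with a window of ±2 days (Protocol 7.5 and 7.6). That is day 19 to 23 or day 26 to 30 after the previous infusion. If two successive visits used opposite ends of their windows, the earliest would be 21 − 4 = 17 or 28 − 4 = 24 days. All are beyond day 10. In a 36-week wait a subject has 12 CP infusions (21-day) or 9 (28-day), and none has a scheduled in-window sample.

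**Which IMP sample can meet all criteria.** The 2- to 3-day draw contains hemosiderin, haptoglobin, plasma free hemoglobin and Coombs (Protocol 6.9), but not blood hemoglobin. Day 7, when the general and hemolysis panels coincide, is the only scheduled point at which every criterion can be met.

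**Coverage of IMP infusions by a Day 7 panel.** Inputs are 15 subjects in Groups 1 and 2 and about 60 in Group 3 (35 in Cohort 1, 25 in Cohort 2). The calculation assumes full completion and all subjects on one cycle; the real mix lies between the two columns.

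| | 21-day cycle | 28-day cycle |
|---|---|---|
| Groups 1 and 2, per subject | 6/17 = 35.3% | 5/13 = 38.5% |
| Group 3, per subject | 2/17 = 11.8% | 2/13 = 15.4% |
| Cohort 1 | (15×6 + 35×2)/(50×17) = 160/850 = 18.8% | (15×5 + 35×2)/(50×13) = 145/650 = 22.3% |
| Cohort 2 | (25×2)/(25×17) = 50/425 = 11.8% | (25×2)/(25×13) = 50/325 = 15.4% |
| All 75 | (15×6 + 60×2)/(75×17) = 210/1275 = 16.5% | (15×5 + 60×2)/(75×13) = 195/975 = 20.0% |
| CP | 0% | 0% |

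**Effect of dividing by all IMP infusions.** The laboratory-detected rate shrinks by 1275/210 = 6.1 or 975/195 = 5.0 overall. In Group 3 it shrinks by 17/2 = 8.5 or 13/2 = 6.5.

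**Illustration.** The documents give no hemolysis rate. Assume 1% per infusion on both products (range 0.5% to 2%), every event visible at Day 7, and no symptom-triggered detection.

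- 28-day cycle: 975 × 0.01 = 9.75 true IMP events (4.9 to 19.5), of which 195 × 0.01 = 1.95 (0.98 to 3.9) are detected. Per all infusions this is 0.20% (0.10% to 0.40%).
- 21-day cycle: 12.75 true events (6.4 to 25.5), of which 2.1 (1.05 to 4.2) are detected. Per all infusions this is 0.16% (0.08% to 0.33%).
- CP: no detection from scheduled samples at any rate.
- Percentage of subjects with a detected event, 1 − 0.99^k at 1%, where k is the number of assessed infusions: Groups 1 and 2, 5.9% (k = 6) or 4.9% (k = 5); Group 3, 2.0% (k = 2). If every infusion were assessed it would be 15.7% or 12.2%.

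**Markers.** The list begins "increased reticulocyte count, increased LDH, low haptoglobin". Reticulocyte count is in neither the hematology panel of Protocol 6.8 nor the hemolysis panel of 6.9. It is also absent from the analytes named for the additional listing in SAP 11.5.1.

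**The case against.** CP is not unobserved. Every CP infusion is followed by a 1-hour examination for signs of hemolysis, with a work-up if positive, and by calls at 24 and 72 hours that can lead to one at the investigator's discretion (Protocol 6.12). All of these fall inside the 10-day window, and SAP 11.5.3 summarizes the signs and work-up results. A reader who infers that CP cases are impossible goes too far. But the same route operates on IMP, so it does not offset the Day 7 panels. It also follows local practice, which the documents do not itemize. The laboratory trigger for a work-up is a fall of at least 2.0 g/dL, while a case needs only 1 g/dL, so a symptom-free fall between the two on CP would be missed.

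A reader might also infer that the IMP rate has the wrong denominator. The documents do not support that: SAP 11.5.1 states none, and the dilution arises only if all infusions are used. With percentage of subjects, each Group 3 subject who has both draws is assessed twice, and what remains is unequal opportunity for detection.

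Nor do the documents establish that the marker rule is in practice two of five. A local work-up may include reticulocytes.

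Three limits on the consequence stand. The display is descriptive, and Protocol 12.3.4 rules out formal comparison. Events are likely to be few, and two or more confirmed hemolytic events put IMP on hold (Protocol 8.1). The CP versus IMP bias runs against the sponsor's product. It is also fair that the purpose in Protocol 3.1 concerns adverse event data and does not promise a CP rate under the laboratory definition. None of this makes the two columns comparable, and no caveat is planned.

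**Conclusion.** The point holds as a difference in ascertainment together with an unspecified denominator. Scheduled in-window testing covers no CP infusions and about 16.5% to 20% of IMP infusions. Within IMP, coverage is 35% to 38% in Groups 1 and 2 and 12% to 15% in Group 3. With equal true rates the table would tend to favor CP over IMP, and could make children look safer than adults, for reasons of testing alone.

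The coverage figures assume the planned group sizes, full completion and a single cycle length. The 5- to 6-fold dilution is conditional on dividing by all infusions. The expected event counts rest on an assumed rate and show scale only. The lack of a formal test limits the harm but does not remove the misleading display. This should be corrected before the tables are produced.

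**What to change.** In SAP 11.5.1:

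- Use as denominators the subjects and the infusions with hemoglobin, Coombs and marker results within 10 days.
- Show the number assessed by period and, within IMP, by Groups 1 and 2 versus Group 3, alongside the planned cohort and age-group split.
- Report cases found at scheduled samples separately from cases found by symptom-triggered or unscheduled work-up.
- Keep the CP column, since Protocol 12.3.4 commits to showing safety endpoints measured in both periods side by side, but label it 'not systematically assessed; work-up-triggered events only'.
- Keep reticulocyte count in the definition, with a footnote that it is in no scheduled panel. Deleting it would depart from Protocol 12.3.4, and adding the test would be a change of testing beyond the SAP.

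The cost is SAP and table-shell wording and a few extra denominator columns, with no new visits or samples. The downside is that no CP hemolysis rate comparable with IMP can be quoted.

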11.5.2. Clinical Signs of Thrombosis Data

The clinical signs of thrombosis data will be summarized by post dose hours evaluated. Twenty-four hours post infusion, subjects will be contacted by phone calls. The results of thrombosis testing results will be summarized when a full work-up is necessary. The clinical signs of thrombosis data will also be listed.

11.5.3. Clinical Signs of Hemolysis Data

The clinical signs of hemolysis data will be summarized by post dose hours evaluated. Twenty-four hours post infusion, subjects will be contacted by phone calls. The results of hemolysis testing results will be summarized when a full work-up is necessary. The clinical signs of hemolysis data will also be listed.

11.5.4. β 2GPI and to β 2GPI-DI Antibody Data

Data on formation of antibodies to β 2GPI (IgG and IgM) and to β 2GPI-DI (IgG) will be tabulated and listed.

11.5.5. Safety Laboratory Data

Safety laboratory parameters will be graded according to FDA guidance Toxicity Grading Scale for Healthy Adult and Adolescent Volunteers Enrolled in Preventive Vaccine Clinical Trials and summarized using descriptive statistics at baseline and at each subsequent time points. Those lab parameters that are not defined in the FDA guidance will be summarized descriptively.

All laboratory results will be tabulated for the safety population.

All laboratory results will be provided as a listing, and any values that lie outside the normal range or are clinically significant will be flagged.

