1.3 Benefit/Risk Statement

Because of advances in our medical understanding and treatment of PIDD, patients who in the past would not have survived childhood are now able to live nearly normal lives with the lifelong administration of IGIV infusions. In subjects with a compromised immune system, prophylactic treatment with IGIV has been shown to increase the time between serious bacterial infections, decrease the incidence of overall bacterial infections, and reduce the number of hospitalizations required for treatment of infections (Boyle and Buckley, 2007; Bruton, 1952; Eijkhout et al., 2001; Roifman & Gelfand, 1988).

Replacement immunoglobulin given either IV or SC is standard practice for subjects with PIDD. Most patients receive IGIV infusions at intervals of 2, 3, or 4 weeks. Patients receiving subcutaneous treatment receive treatment weekly. Reductions in hospitalization and infection rates have been well documented in subjects receiving high doses (>400 mg/kg every 3 weeks) of IGIV; and maintaining trough levels of IGIV above 5 mg/mL is considered standard of care (Boyle and Buckley, 2007; Eijkhout et al., 2001; Roifman & Gelfand, 1988).

ProMetic's Immune Globulin (Human) Intravenous 10% solution is analytically comparable to currently marketed IGIV products that are widely used by patients with PID. ProMetic's IGIV is expected to provide similar therapeutic benefits as commercially available IGIV products. Since the levels of Anti-A/Anti-B hemagglutinins have been reduced by exposure to an Anti-A/Anti-B column, less hemolytic events may be expected with the ProMetic IGIV.

The following adverse reactions are known to be associated with IGIV products: chills, headache, fever, vomiting, allergic reactions, infusion site reactions, nausea, arthralgia, low blood pressure, and moderate low back pain. Rarely, human normal immunoglobulins may cause a sudden fall in blood pressure and, in isolated cases,

anaphylactic shock, even when the patient has shown no hypersensitivity to previous administration. Cases of reversible aseptic meningitis, isolated cases of reversible hemolytic anemia/hemolysis, and rare cases of transient cutaneous reactions have been observed with human normal immunoglobulin. An increase in serum creatinine level and/or acute renal failure has been observed.

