4.3.2 Exclusion Criteria

1. Subject has secondary immunodeficiency or has been diagnosed with dysgammaglobulinemia or isolated IgG subclass deficiency.
2. Subject has ever had a history of severe anaphylactic or anaphylactoid reaction to immunoglobulins or other blood products.
3. Subject has a known history of immunoglobulin A (IgA) deficiency and known anti-IgA antibodies. (Note that subjects with IgA deficiency without known antibodies to IgA may be enrolled.)
4. Subject has had a thrombotic event, such as deep vein thrombosis, myocardial infarction, cerebrovascular accident, pulmonary embolism, at any time.
5. Subject has received blood products except IGIV, IGSC, or albumin within the previous 12 months.
6. Subject has participated in another study (except for IGIV, IGSC studies) within the previous 4 weeks.
7. Subject has had cancer in the past 5 years, except for basal cell or squamous cell cancers of the skin.
8. Subject has current or prior diagnosis of malignancies of lymphoid cells such as lymphocytic leukemia, non-Hodgkin's lymphoma, or immunodeficiency with thymoma.
9. Subject has known hypoalbuminemia (<3 gm/dL), protein-losing enteropathy, or nephrotic syndrome.
10. Subject has had a documented active infection within 7 days prior to Screening, or subject is on continuous prophylactic antibiotics. Subjects receiving a course of antibiotic treatment for a recent bacterial infection, which is controlled, can be enrolled into the study.
11. Subject is positive for human immunodeficiency virus (HIV)-1 or HIV-2.
12. Subject has a positive hepatitis C virus (HCV) or hepatitis B virus (HBV) nucleic acid test (NAT) performed either by qualitative or quantitative polymerase chain reaction (PCR) in the past 12 months.
13. Subject has levels of alanine aminotransferase (ALT) or aspartate aminotransferase (AST) >2.5 times the upper limit of normal (ULN).
14. Subject has serum creatinine >1.5 times the ULN or a severe chronic condition such as renal failure with proteinuria.
15. Subject has anemia with a hemoglobin level ≤ 8 g/dL.

16. Subject has severe neutropenia with neutrophil count ≤ 1000 per mm^3 or has lymphopenia with < 500 per mm^3 .

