5.2 Safety Endpoints

Safety will be evaluated via the following assessments:

- All reported AEs
- Rate (per subject per infusion), severity, and relatedness of AEs
- Frequency of temporally associated AEs
- Infusional AEs
- Assessment of local tolerability to IMP infusions: Reactions at infusion site
- Adverse reactions/suspected adverse reactions
- Vital sign changes, including changes in systolic and diastolic blood pressure, heart rate, respiratory rate, and body temperature
- Changes from Screening in physical examination findings
- Changes from Baseline in laboratory parameters (blood chemistry, hematology, urinalysis, hemolysis, d-dimer, protein S, and protein C concentrations, titers of antibodies to $\beta 2\text{GPI}$ and $\beta 2\text{GPI-DI}$)
- Frequency of clinical signs of hemolysis and/or thrombosis within 72 hours after infusion of the IMP
- IGIV-associated hemolysis
- Changes from Screening in viral safety markers (HAV, HBV, HCV, HIV-1, HIV-2, and B19)
- Comparisons of safety variables during treatment with IMP and during the Waiting Period on commercial product will be made as described in Section 12.3.4.

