10.1 Definitions

10.1.1 Adverse Event

An AE is any untoward medical occurrence (whether or not considered to have a causal relationship to IMP) in a study subject administered an IMP. Therefore, an AE can be any unfavorable and unintended sign (including a clinically significant laboratory finding), symptom, or disease temporally associated with the use of an IMP, whether or not related to the IMP. For the purposes of this protocol, all AEs occurring during the study are considered treatment-emergent AEs (TEAEs) associated with the use of the immunoglobulin product (either IMP or CP), whether or not the AE is determined to be product related.

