10.3 Eliciting and Reporting of Other Adverse Events

AEs will be captured from signing of Informed Consent/Assent to until 21±4 days or 28±4 days following the last infusion. AEs and ADRs will be elicited and reported as follows:

The condition of the subject will be monitored throughout the study. At each visit, AEs will be elicited using a standard non-leading question such as "*How have you been since the last visit / during the previous study period?*" AEs will also be elicited through the use of Subject Diary cards, which the Investigator will review in detail with the subject at each visit, ensuring accuracy and completeness of entries recorded by the subject.

The staff will also ask specific questions during phone calls to determine whether a work-up for hemolysis and/or thrombosis is necessary. During the phone calls, the staff will ask open-ended questions about the subject's wellbeing and to ensure that AEs are being documented in the Subject Diary. The study staff will review these specific questions with the subject and ensure subject is completing the diary. (Section 6.12.3)

Any AE or ADR occurring during the study will be noted in detail on the appropriate pages of the eCRF. If the subject reports several signs or symptoms, which represent a single syndrome or diagnosis, the latter should be recorded in the eCRF. The Investigator will grade the severity of all AEs or ADRs (mild, moderate, or severe), the seriousness (non-serious or serious) and relatedness, with final determination of causality established by the Sponsor, as defined in Section 10.1.

In the event of abnormal laboratory findings considered clinically significant by the Investigator, the tests will be repeated and followed-up, as needed. Diseases, signs and symptoms, and/or laboratory abnormalities already existing before the first administration of IMP are not considered as AEs when observed at a later stage unless they represent a worsening.

The Investigator should always provide detailed information concerning any abnormalities and the nature of, and reasons for any necessary action(s), as well as any other observations or comments, which are useful for the interpretation and understanding of the subjects' AEs or ADRs.

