12.3.4 Safety Endpoints

Evaluation of safety includes the analyses of laboratory investigations, adverse events, and adverse reactions/suspected adverse reactions. No formal statistical analyses will be done comparing any of the safety endpoints between the Waiting Period on commercial product and the IMP treatment period. However, all safety endpoints measured during both the Waiting Period on commercial product and the IMP treatment period will be summarized side-by-side using the appropriate descriptive statistics. For the Waiting Period on commercial product, the summary descriptive statistics will be aggregated over all commercially licensed products.

Laboratory Data:

A summary by treatment period (Waiting period, IMP treatment period) will be produced for each of the laboratory parameters at each visit. These safety summaries will include descriptive summary tables and the data will be summarized in the form of frequency count, mean, standard deviation, median, minimum and maximum by treatment period and visit.

Adverse Events:

The seriousness, severity and relationship to the study drug of adverse events (AEs) will be observed and recorded on repeated administrations of the study drug using the MedDRA dictionary for the coding of AEs and serious adverse events (SAEs).

The number and proportion of subjects who have one or more AEs will be tabulated by seriousness, severity, and relationship to treatment according to body system and treatment period. Temporally related AEs will be similarly summarized. Rates of AEs will be estimated on a per infusion per subject basis and tabulated by seriousness, severity, and relationship to treatment according to body system and treatment period.

The following observations will be summarized, using the standard set of summary statistics (see 12.3.1).

- The number of infusions administered

- The total number of AEs experienced (irrespective of causality)
- The total number of AEs temporally associated with infusions
- During the infusion
- Within 1 hour after the infusion
- Within 24 hours after the infusion
- Within 72 hours after the infusion
- The number and proportion of infusions with which one or more infusional AEs are associated
- The number of infusional AEs per infusion
- Rate-related AEs

AEs will also be tabulated for the 30 subjects who received the highest doses of IMP and commercial product.

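### For chemistry, hematology and urinalysis, no planned summary gives change from the subject's own pre-IMP value or the share of subjects who worsened, although Protocol 5.2 makes change from Baseline a safety endpoint

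*SAP*

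**What the plan says.** The endpoint is in Protocol 5.2: "Changes from Baseline in laboratory parameters (blood chemistry, hematology, urinalysis, hemolysis", followed by further markers.

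The analysis text is narrower.

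- Protocol 12.3.4 (Laboratory Data) gives count, mean, SD, "median, minimum and maximum by treatment period and visit".
- SAP 11.5.5 applies a published toxicity grading scale for healthy adult and adolescent volunteers. Results are then "summarized using descriptive statistics at baseline and at each subsequent time points". Parameters the scale does not cover get descriptive summaries. All results are to be tabulated for the safety population, with no layout given, and listed with abnormal or clinically significant values flagged.
- SAP 6.1 defines descriptive statistics for continuous variables as number of observations, mean, SD, median, minimum and maximum. Change is not among them.

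Two other routes touch laboratory data. SAP 11.5.1 defines a composite hemolysis event. It also plans a listing of hemolysis analytes over time, including LDH and bilirubin, for subjects whose hemoglobin falls by more than 1 g/dL from the mean of their Screening and pre-IMP values. The AE definition in Protocol 10.1.1 covers any unfavourable sign, "including a clinically significant laboratory finding". Under Protocol 10.3, laboratory abnormalities present before the first IMP dose "are not considered as AEs when observed at a later stage unless they represent a worsening".

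**The concern.** The endpoint is a within-subject change, and the planned tables show levels at separate visits. In a single-arm study the subject's own pre-IMP value is the natural comparator, and a by-visit table does not use it. The minimum and maximum at a visit show the extreme value. They do not show what that subject's value was before IMP, or whether the same subject recurs at later visits.

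This matters because subjects may enter with abnormal values. ALT or AST excludes only above 2.5 times ULN, and the creatinine criterion is "Subject has serum creatinine >1.5 times the ULN". Values between ULN and those limits are therefore admissible, so out-of-range results on IMP can include abnormalities that were there at entry. Creatinine is a parameter for which the distinction counts. On IGIV products generally, Protocol 1.3 says: "An increase in serum creatinine level and/or acute renal failure has been observed".

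At stake is a descriptive safety statement for the study report: how many subjects worsened from their own starting point, parameter by parameter.

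**Working it through.** The plan gives no figure on this point, so there is none to reproduce. The check has three parts.

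**1. Does any planned output deliver the endpoint?**

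- Protocol 12.3.4 and the SAP 11.5.5 summaries: levels by visit or time point. No change, no shift, no worst value per subject.
- SAP 11.5.5 tabulation sentence: no layout, so it commits to neither a change table nor a shift table.
- SAP 11.5.5 listing: every result, arranged by subject under SAP 6.1. The information is there, but no count is.
- SAP 11, side-by-side summaries of the CP and IMP periods: no change or shift is specified.
- SAP 11.2, maximum grade per subject: applies to AEs by preferred term, not to laboratory results.
- SAP 11.5.1, composite event: the hemoglobin fall is measured from the previous value, not from Baseline.
- SAP 11.5.1, listing: referenced to pre-IMP values, but triggered by hemoglobin and limited to hemolysis analytes. Creatinine, BUN, ALT, AST, WBC and platelets (all collected under Protocol 6.8) are outside it.

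None summarizes change from the pre-IMP value, or the share of subjects who worsened, for the three panels.

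**2. How many post-baseline draws are scheduled on IMP?** (Protocol 6.8; TCTV is Infusion 13 on the 28-day cycle and Infusion 17 on the 21-day cycle.)

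- Pre-infusion, 28-day: Infusions 2, 3, 4, 8, 12, TCTV, LTSV = 7. The 21-day cycle adds Infusion 16 = 8.
- Day 7, Group 3: after Infusions 1 and 4 = 2. Totals: 7 + 2 = 9 (28-day) and 8 + 2 = 10 (21-day).
- Day 7, Groups 1 and 2: after Infusions 1, 2, 4, 8, 12 = 5 (28-day), plus 16 = 6 (21-day). Totals: 7 + 5 = 12 and 8 + 6 = 14.
- Shared by every group and cycle: Infusions 2, 3, 4, 8, 12, TCTV, LTSV, and Day 7 after Infusions 1 and 4 = 9.

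**3. What can by-visit rows leave undetermined?** Illustration only, not evidence about this trial. Assume exactly one affected subject in each of the 9 shared rows, and all N subjects present in every row. N is the planned enrolment. The number of subjects ever affected after baseline lies between 1 (the same subject throughout) and 9 (a different subject each time):

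- Cohort 2, N about 25: 1/25 = 4.0% to 9/25 = 36.0%
- Cohort 1, N about 50: 1/50 = 2.0% to 9/50 = 18.0%
- Pooled, N about 75: 1/75 = 1.3% to 9/75 = 12.0%

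The number who worsened from their own pre-IMP category depends also on the baseline row, which the SAP does plan to show.

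- If that row is clean, at least one subject must have worsened, so the range is 1/N to 9/N.
- If it shows one affected subject, the range is 0/N to 9/N. Zero arises when that subject simply stays affected. Nine arises when that subject recovers before the first later draw and nine others are affected once each.

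So the 0/N and 9/N cases share the same post-baseline rows. They share the baseline row as well only if a tenth subject is involved.

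**The case against.** The strongest reply is that this is unspecified detail, not an unserved endpoint. The SAP says it supplements the protocol, the protocol names the endpoint, and SAP 11.5.5 promises that all results will be tabulated. The listing shows every subject's values in sequence for about 75 people. For subjects with complete data, mean change equals the difference between the baseline and visit means. Clinically significant findings, and worsening of earlier abnormalities, become AEs and are tabulated per subject by worst severity under SAP 11.2. A clinically significant creatinine rise would therefore be counted.

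Much of this stands. It rules out several stronger readings that a reader might infer:

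- That the SAP has no subject-level or baseline-referenced laboratory output. The SAP 11.5.1 hemolysis listing is one.
- That important laboratory harm would go unreported. The AE route and the flagged listings cover it, subject to investigator judgment in an open-label study.
- That the by-visit toxicity grades necessarily mix entry abnormalities with new ones. The scale's cut-offs are not in the documents, so whether ALT below 2.5 times ULN or creatinine below 1.5 times ULN attracts a grade is unknown. The mixing is certain only against the normal range.

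What does not stand is the claim that the endpoint is delivered. A tabulation without a layout is not a plan for change from Baseline. A difference of means gives neither the spread of change nor the number who worsened, and it is only approximate when denominators differ. A listing leaves the reader to count by hand. The AE route counts only what the investigator judged to be an AE.

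**Conclusion.** The point holds as a gap between a named safety endpoint and the analyses specified for it. The gap begins in Protocol 12.3.4, and SAP 11.5.5 carries it forward. Followed as written, the plan produces no summary of change from the subject's pre-IMP value, and no count of subjects who worsened, for chemistry, hematology or urinalysis. What stays uncounted is worsening that the investigator does not record as an AE.

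The documents give no abnormality rates, so the practical size cannot be estimated. The 4.0% to 36.0% range for Cohort 2, and its counterparts, rest on an arbitrary one affected subject per row with complete data; they show only what by-visit rows cannot distinguish. The matter is descriptive and does not touch the primary efficacy analysis. It should be corrected before the final tables are programmed, but it does not undermine the trial.

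**What to change.** In SAP 11.5.5 add, by cohort:

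1. For continuous parameters, descriptive statistics of change from the last pre-IMP value at each IMP visit.
2. A per-subject shift table for each parameter, from the last pre-IMP category to the worst category after IMP Infusion 1, through the LTSV sample drawn before standard IgG. Use toxicity grade where the scale defines one and low/normal/high otherwise. Give the number and percentage of subjects who worsened.

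Name the last pre-IMP value explicitly, because Protocol 6.8 attaches the baseline label to Infusion 1 of either IMP or CP. Take as denominator the IMP recipients with a pre-IMP value and at least one later value, since the SAP 5.2 safety population also admits subjects who received only CP. Include unscheduled values in the shift table and say so in SAP 6.4, which otherwise works by nominal visit. Keep the by-visit tables and listings.

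The cost is SAP wording and a few extra tables from data already collected. Per-subject worst-case rates will look less favourable than by-visit rates. Worst category also tends to rise with the number of draws, so a footnote should state that Groups 1 and 2 have 12 to 14 scheduled post-baseline draws against 9 to 10 in Group 3.
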